9.4 Minimization of Risk

Risks have been minimized by designing the device under evaluation (total knee arthroplasty surgical instruments) to be similar to commercially available total knee arthroplasty surgical instruments used for the same indication. The ATTUNE surgical instruments have been functionally tested to verify performance characteristics and biocompatibility. In addition, only trained orthopaedic surgeons with expertise in treating this condition will participate in this study.

Investigators should refer to the ATTUNE implant system package insert for additional information and instructions for use (Appendix D) and the surgical technique (Appendix B).

The Sponsor will further minimize the identified and/or emergent risks throughout the study, by reviewing the reported complications and adverse effects. All SAEs, SADEs, ADEs, UADEs and USADEs will be reviewed and evaluated by the Medical Monitor assigned to this project.

9.5 Benefit Analysis

There are no potential benefits to study Subjects from participation in this study. The knowledge gained from this investigation may help future TKA patients.

9.6 Adverse Event

9.6.1 Categories and Definitions

Table 9-1: Adverse Event Categories

ADVERSE EVENTS	Non-Device Related	Device- and/or Procedure-related	
Non-Serious	Adverse Event (AE)	Adverse Device Effect (ADE)	
Serious	Serious Adverse Event (SAE)	Serious Adverse Device Effect (SADE)	
		Anticipated	Unanticipated
		Anticipated Serious Adverse Device Effect (ASADE)	Unanticipated Serious Adverse Device Effect (USADE)

Table 9-2: Adverse Event Definitions

Term	Details
Adverse Event (AE)	Any untoward medical occurrence, unintended disease or injury, or untoward clinical signs (including abnormal laboratory findings) in subjects, users or other persons, whether or not related to the investigational medical device. Adverse Event is synonymous with complication or medical event.

Term	Details
Serious Adverse Event (SAE)	
An Adverse Event that:
 
 leads to death, leads to a serious deterioration in the health of the subject that 
 ○ resulted in a life –threatening illness or injury, ○ resulted in an impairment of a body structure or a body function, required in-patient hospitalization or prolongation of existing hospitalization, resulted in medical or surgical intervention to prevent permanent impairment to body structure or a body function, leads to fetal distress, fetal death or a congenital abnormality or birth defect. 
Note: Planned hospitalization for a pre-existing condition, or a procedure required by the CIP, without serious deterioration in health, is not considered a serious adverse event.

Adverse Device Effect (ADE)	An adverse event related to the use of an investigational medical device. This definition includes any event resulting from insufficiencies or inadequacies in the instructions for use or the deployment of the device. This definition includes any event that is a result of a user error.
Anticipated AE	An effect which by its nature, incidence, severity or outcome has been previously identified in the Instructions for Use for the medical device.
Anticipated Adverse Device Effect (AADE)	An adverse event related to the use of an investigational medical device is previously identified in nature, severity, or degree of incidence in the current version of the Instructions for Use. This definition includes any event resulting from insufficiencies or inadequacies in the instructions for use or the deployment of the device. This definition includes any event that is a result of a user error.
Unanticipated Adverse Device Effect (UADE)	An adverse event related to the use of an investigational medical device not previously identified in nature, severity, or degree of incidence in the current version of the risk analysis report. This definition includes any event resulting from insufficiencies or inadequacies in the instructions for use or the deployment of the device. This definition includes any event that is a result of a user error.
Serious Adverse Device Effect (SADE)	An adverse event related to the use of an investigational medical device that has resulted in any of the consequences characteristic of a serious adverse event.
Anticipated Serious Adverse Device Effect (ASADE)	A serious adverse device effect which by its nature, incidence, severity or outcome has been identified in the current version of the Instructions for Use/risk analysis report. This definition includes any event resulting from insufficiencies or inadequacies in the instructions for use or the deployment of the device. This definition includes any event that is a result of a user error.

Term	Details
Unanticipated Serious Adverse Device Effect (USADE)	A serious adverse device effect which by its nature, incidence, severity or outcome has not been identified in the current version of the risk analysis . This definition includes any event resulting from insufficiencies or inadequacies in the instructions for use or the deployment of the device. This definition includes any event that is a result of a user error.
Site Awareness (Date of AE Awareness)	The day, month and year that the study site becomes aware of information from any source that reasonably suggests that an Adverse Event has occurred. Note: This date may or may not correspond to the date of onset. The date of awareness is critical to reporting timelines (see Section 9.8).

9.7 Adverse Event Reporting Guidelines

9.7.1 AE Reporting by Site to the Sponsor

For AEs to be reported through this protocol, a record including details of site awareness, the nature, onset, duration, seriousness, relationship to the device, relationship to the procedure, treatment given (if any) and outcome, will be entered into the subject's eCRF.

[figure not shown]
For this study, only serious AEs and those AEs related or possibly related to either the device and/or the procedure are to be reported to the SPONSOR (Please see Figure 9-1).

The outer circle (Figure 9-1) represents all AEs that could possibly be observed. For this protocol, not all AEs are required to be reported. The below list are the reportable AE's that must be recorded on the eCRF and submitted to the Sponsor by entering into EDC per the reporting timelines detailed below:

- Any AE classified as '**Serious**' (SAEs, SADEs, SUADEs) to include Serious procedure related AEs – report to Sponsor as soon as able but **no later than 72 hours from site awareness***.
- All UADEs – report to Sponsor as soon as able but **no later than 72 hours from site awareness***.
- All non-Serious Device Related (ADE) – report to Sponsor as soon as able but **no later than 2 weeks from site awareness***.
- All non-Serious Procedure Related AEs, except for selected events (see Exhibit E-2: Non-reportable list) - report to Sponsor as soon as able but **no later than 2 weeks from site awareness***.

***NOTE: Not meeting the above reporting timelines to the Sponsor will result in a protocol deviation.**

Figure 9-1: Adverse Event Reporting for this Study Protocol

Pre-existing medical conditions or symptoms reported prior to the surgical event are not to be recorded as AEs^E. The only exception would be in the event there is an exacerbation of a pre-existing medical condition or symptom(s) in the post-operative time frame, then an AE must be reported.

AEs are reported beginning from surgery and until Subject participation has ended (study completed or consent withdrawn). AEs must be followed to resolution, or until the study completion or consent withdrawal. When a Subject ends participation in the study (either study completion or consent withdrawal) an AE must be designated either as “resolved” (end date must be provided), or as “ongoing.”

Subjects should be encouraged to report AEs spontaneously and may volunteer AE information at any time. At each evaluation, the Investigator will determine whether a study reportable AE has occurred. If it is determined that such an AE has occurred, the Investigator should obtain all the information required to complete the appropriate AE form eCRF. If an event occurs at an outside institution, the Investigator should attempt to obtain, if possible, required AE information.

The Investigator will record the nature, severity, treatment and outcome of the AE, and will determine their association to the device and/or the study procedure.

^E An example could be pre-existing contralateral knee osteoarthritis with a planned TKA intervention after the index knee surgery.

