2.1 Time and Events Table

Event / Visit	Pre-Op	Surgery	Post-Op
Required Timing (days)	-180d to include day 0	0	30 -150
Discuss Study with Subject	Yes		
Screening Log	Yes		
Informed Consent	Yes		
Enrollment	Yes		
Complete Subject History eCRF	C		
Surgical Procedure 
 Complete Operative Details eCRF Complete Device Log eCRF 		C C	
Radiographs 
 Hip to Ankle Long Film 			R*

 AP View 	R		R

 Lateral View 			R
Complete Adverse Event eCRF		A	A
Complete End of Study/Withdrawal	A	A	C
Advise the Subject when they will next be seen	Yes	Yes	
C= Case Report Form to be completed and submitted in the Electronic data capture system R= Radiograph obtained and submitted R*, For the purposes of this investigation this radiograph will only be performed when the Subject can achieve full leg extension ($\pm 5^\circ$). A= As needed			

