8.3.4 Post-operative Management

Immediate post-operative management is at the discretion of the Principal Investigator and should follow each Site's standard of care.

The one(1) postoperative study follow-up visit will be conducted according to the Time and Events Table 2.1. Each Investigator or designee will collect information as noted in Table 8-4 below. At this visit radiographs will be collected as detailed in the Radiographic Protocol (Exhibit F). An independent radiographic reviewer (IRR) will evaluate all radiographs. Copies of the evaluations will be available to Investigators upon request.

Table 8-4: Post-operative Data Collection and eCRFs

Evaluation	Details of Evaluation
Radiographs	For all Subjects post-operative radiographs will be obtained.
End of Study Completion or Subject Withdrawal	For all Subjects the Investigator or designee must complete an End of Study/Subject Withdrawal eCRF to confirm the Subject is no longer in the study.
Post-operative Complication(s) (if applicable)	In the event of a post-operative complication an Adverse Event eCRF is completed. A post-operative complication is defined as a complication that occurs at any time from the time the Subject is in the recovery room up through the time a Subject withdrawal form is submitted ending the Subject's study participation. Complete a separate form for each post-operative complication.

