10.4 Interval Windows

The pre-operative window will be from 180 days prior to surgery up to the day of surgery, which is defined to be Day 0. The 3 month post-operative interval will be defined as 90 days plus or minus 60 days.

Table 10-1: Interval Windows

Follow-up [days]			
Pre-Op	Surgery	Immed Post-op	3 Month
-180 to 0	0	1 to 29	30 to 150

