10.6 Primary and Secondary Endpoints

The primary endpoint in this study is mechanical axis alignment, and the primary endpoint analysis will be to determine whether the alignment achieved with SUI instrumentation is non-inferior to the alignment achieved with RUI instrumentation. Mechanical axis alignment is defined as the angle between the line drawn from the center of the femoral head through the center of the knee and line drawn from the knee center to the ankle center. Mechanical axis alignment will be measured from weight bearing long-leg (51") Anteroposterior (AP) radiographs, taken approximately 90 days post-op (when Subject has reached full knee extension, within 5 degrees) and read by an independent radiographic reviewer. The non-inferiority margin was set at 1.5° because the study team felt this was the maximum non-meaningful difference when thinking about absolute mechanical axis alignment differences between the RUI and SUI groups. A standard deviation between 1.5° to 2° is anticipated based on previous studies conducted by the sponsor that had the same primary endpoint (Protocol ID #'s 04023, 08003).

The secondary endpoints are as follows:

- To compare alignment achieved with SUI vs. RUI of individual components in the frontal and sagittal planes, specifically: distal femoral varus-valgus (FM) , proximal tibial varus-valgus (TM), femoral component flexion and tibial slope.
To compare the type and frequency of adverse events, from the time of consent through to withdrawal of a Subject or the end of the study (includes pre-operative, intraoperative and early postoperative device-related adverse events), between the SUI and RUI instrument groups.

Exploratory endpoints

- To compare SUI and RUI operating room times. Specifically the duration of the four key steps in the procedure (possibly overlapping) will be compared. See Table 8-3.
- To determine whether SUI provides opportunity to reduce the incidence of minor procedural obstacles during the time in the OR.
- To compare Surgeon satisfaction of SUI instrumentation to RUI instrumentation.

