10.10 Analysis Plan

The primary endpoint is a non-inferiority test of mean absolute mechanical axis angle, comparing single use and reusable instrument results with a non-inferiority margin of 1.5° using a 1-sided independent means t-test and $\alpha = 0.05$. The primary endpoint analysis null hypothesis will be rejected and non-inferiority will be concluded if the 1-sided upper 95% confidence limit for $\mu_{SUI} - \mu_{RUI}$ is less than 1.5°.

Preoperative demographics will be compared to determine whether differences exist between treatment groups. Age and BMI will be compared using two-tailed independent means t-tests. Gender distribution will be compared with a Fisher's exact test.

Secondary analyses include:

- Tests of differences for individual component alignment in the frontal and sagittal planes, specifically: distal femoral varus-valgus (FM), proximal tibial varus-valgus (TM), femoral component flexion and tibial slope using (independent means two-tailed t-tests).
- The types and frequencies of adverse events will be tabulated for all enrolled knees. The proportion of each complication will be compared using a Fisher's Exact Test (2 x 2 only) and Chi-square.

Exploratory analyses will be conducted to see if SUI improves OR efficiency compared to conventional (RUI) instruments. Exploratory analyses will also be conducted to investigate OR step times, inter-site differences in OR times, and issues that potentially introduced delays or interruptions in the surgical flow.

The Following Table presents a summary of the planned statistical tests:

Table 10-2: Planned statistical comparisons

Comparison	Purpose	Expected Result
Mean absolute mechanical axis non-inferiority	Primary efficacy	SUI Non-inferior to RUI
Demographic comparisons	Test comparability	No difference
Distal Femoral Varus-Valgus (FM)	Secondary efficacy	No difference
Proximal Tibial Varus-Valgus (TM)	Secondary efficacy	No difference
Femoral flexion	Secondary efficacy	No difference
Tibial slope	Secondary efficacy	No difference
OR Efficiency	Exploratory Analysis	No difference

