## **8.5 Safety Analyses**

For this study, only serious AEs and those AEs related or possibly related to either the device and/or the procedure are to be reported to the Sponsor (Please see Figure 9-1 in the CIP). AEs were collected from the time of surgery forward and coded by MedDRA v17.0.

An adverse event overview table will be provided and will include both the number of events (n) and the number and percentage (n, %) of subjects with 1 or more event in the following categories:

- Serious,
- Definitely, probably, or possibly device-related,
- Definitely, probably, or possibly procedure-related,
- Operative site,
- Systemic,
- Intra-operative (AE with onset on the day of surgery), and
- Post-operative (AE with onset after the date of surgery).

In addition, all adverse events will be listed.

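### Compliant subjects can be observed for adverse events for anything from 30 to 150 days, but the arms are compared on crude proportions with no common period, so a visit-timing difference between phases could create or hide a difference

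*Protocol*

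**What the plan says.** - **Collection period.** Protocol 9.7.1: "AEs are reported beginning from surgery and until Subject participation has ended (study completed or consent withdrawn").
- **One visit.** Protocol 8.3.4: "The one(1) postoperative study follow-up visit will be conducted according to the Time and Events Table 2.1". At that visit, "the Investigator or designee must complete an End of Study/Subject Withdrawal eCRF to confirm the Subject is no longer in the study".
- **Window.** Protocol 10.4: "The 3 month post-operative interval will be defined as 90 days plus or minus 60 days". SAP Table 4-1 gives the same limits, day 30 to day 150, with target day 90.
- **Link to recovery.** The footnote to Protocol Table 2.1 says of the long film that "this radiograph will only be performed when the Subject can achieve full leg extension", within 5 degrees.
- **Comparison.** Protocol 10.10: "The proportion of each complication will be compared using a Fisher's Exact Test (2 x 2 only) and Chi-square". SAP 8.5 tabulates numbers of events and "the number and percentage (n, %) of subjects with 1 or more event in the following categories". It names no between-arm test, although SAP 8.1 makes Fisher's exact test the convention for categorical variables when a test is needed. SAP 4 brings all safety data into the safety analysis.
- **Status.** Comparing the type and frequency of adverse events is a secondary objective (Protocol 6.2, SAP 1.2). SAP 5 treats every comparison other than the primary as exploratory and rules out labeling claims from them.
- **Start of the period.** Protocol 10.6 counts events "from the time of consent through to withdrawal of a Subject or the end of the study" and mentions pre-operative events. Protocol 6.2, Protocol 9.7.1 and SAP 8.5 start at surgery.

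**The concern.** The percentage of subjects with an event depends on how long they were observed. Here two fully compliant completers can differ five-fold in observation time (150/30 = 5). A randomized trial would tend to even this out between arms. In this design each site completes its RUI cases before its first SUI case, so any drift in visit scheduling between the two phases falls on one arm. The plan has no common cut-off day, no time-to-event estimate and no tabulation of follow-up length that would let a reader see such a drift. The secondary safety comparison could then show a difference that reflects only scheduling, or conceal a real excess with SUI. Because the film waits for full extension, observation length may also depend on how recovery went.

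**Working it through.** **The plan's own figure.** No power or precision is stated for adverse events. The only sample-size figure concerns the primary endpoint: 35 per group, SD 1.87°, margin 1.5°, one-sided alpha 0.05, 95% power. It reproduces (noncentral t with 68 degrees of freedom gives 0.953) and has no bearing on this point.

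**Inputs from the documents.** 44 subjects per group (Protocol 10.9); visit window day 30 to 150 (Protocol 10.4); Fisher's exact test (Protocol 10.10).

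**Assumptions.** The documents give no adverse-event rates and no distribution of visit days. The 90-day risk r, the hazard shape k and the mean visit days are therefore assumed and varied. The true hazard is the same in both arms throughout.

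**Formula.** Expected proportion with an event by day t: P(t) = 1 − (1 − r)^((t/90)^k). Here k = 1 is a constant hazard, and k = 0.5 and k = 0.25 are increasingly front-loaded. Each arm is evaluated at its mean visit day.

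Example with r = 0.10, k = 1: P(60) = 1 − 0.9^(60/90) = 0.068 and P(120) = 1 − 0.9^(120/90) = 0.131. The ratio is 1.93. Out of 44 that is 3.0 against 5.8 subjects expected.

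The last column is the chance of a two-sided Fisher p < 0.05, by exact enumeration at 44 per group.

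| r (90-day risk) | k | Mean visit days | Expected % | Ratio | Fisher p < 0.05 |
|---|---|---|---|---|---|
| 10% | any | 90 vs 90 | 10.0 vs 10.0 | 1.00 | 1.9% |
| 10% | 1 | 75 vs 105 | 8.4 vs 11.6 | 1.38 | 3.4% |
| 10% | 1 | 60 vs 120 | 6.8 vs 13.1 | 1.93 | 8.8% |
| 10% | 0.5 | 60 vs 120 | 8.2 vs 11.5 | 1.39 | 3.5% |
| 10% | 0.25 | 60 vs 120 | 9.1 vs 10.7 | 1.18 | 2.3% |
| 10% | 1 | 30 vs 150 (limits) | 3.5 vs 16.1 | 4.67 | 37.7% |
| 20% | 1 | 60 vs 120 | 13.8 vs 25.7 | 1.86 | 20.0% |
| 20% | 0.5 | 60 vs 120 | 16.7 vs 22.7 | 1.36 | 6.4% |

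For r from 5% to 30% and all three values of k, the spurious ratio at 60 vs 120 days runs from 1.16 to 1.97.

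**Common window.** If both arms are read at day 30, P(30) is identical under equal hazards whatever the visit timing, so the expected difference is 0. The Fisher false-positive probability is then 0.2% to 2.5% for r of 10% and 20% over the three shapes.

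**Events per subject-time.** The cumulative hazard is proportional to t^k, so the average rate is proportional to t^(k−1). For day 120 against day 60 the rate ratio is 2^(k−1): 1.00 at k = 1, 0.71 at k = 0.5 and 0.59 at k = 0.25. At k = 0.25 this is a 1.68-fold distortion (1/0.595), larger than the 1.18-fold distortion of the crude proportion and in the opposite direction.

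**The case against.** The strongest reply is that bias between arms needs visit timing to differ by arm, and nothing in the documents shows that it will. Both arms have the same window, the same day-90 target, the same sites and one surgeon per site. Waiting for full extension applies to both. This stands: the weakness is conditional.

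A reader might infer that SUI subjects, treated last, will be seen earlier because the study is closing. The documents do not support that. The Protocol summary allots 5 months of follow-up after 8 months of enrollment, which is about 150 days and covers the whole window for the last subject.

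Three further replies also hold in part:

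- SAP 8.5 separates events with onset on the day of surgery from later ones. The former are observed equally in everyone and belong to the day the instruments are used.
- The exploratory label and the bar on labeling claims limit the consequences. They do not make percentages over unequal periods comparable.
- Reportable events are limited to serious, device-related or procedure-related ones (Protocol 9.7.1), and a constant hazard to day 150 is only an assumption for these. With front-loading or a moderate shift, the 10% cases stay below a 5% false-positive rate.

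One might also read the end of the study in Protocol 6.2 as the end of the whole trial. Table 2.1, 8.3.4 and 9.7.1 tie the end to each subject's own completion.

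**Conclusion.** The gap is real: observation time may vary five-fold among compliant subjects, the comparison ignores it, and the sequential design offers no protection. Whether it will bias this trial cannot be told from the documents. Its size rests on the assumed risk, hazard shape and timing shift. At a 10% risk it ranges from under one subject in 44 (60 vs 120 days, strongly front-loaded: 4.0 against 4.7 expected) to nearly a doubling at the same shift with a constant hazard. It could act in either direction. The primary endpoint and its sample size are unaffected. This is a worthwhile low-cost improvement to a secondary, exploratory safety comparison. It is not evidence that the comparison will mislead.

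The consent-versus-surgery wording in Protocol 10.6 is a separate editorial inconsistency and adds nothing to the follow-up argument.

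**What to change.** 1. In Protocol 10.10 and SAP 8.5, add a between-arm comparison of subjects with at least one adverse event whose onset is from day 0 to day 30. This is the longest period that every subject seen in window completes. Show by arm how many subjects left before day 30, or use a Kaplan-Meier estimate at day 30, which assumes that those early departures are non-informative.
2. Keep the full-period count and percentage table and the listing. Beside the table, show the distribution of follow-up length by arm.
3. Do not use events per subject-time as the correction. It is valid only under a constant hazard and can distort more than the crude percentage.
4. Separately, reconcile the consent and pre-operative wording in Protocol 10.6 with the surgery wording in Protocol 6.2, Protocol 9.7.1 and SAP 8.5.

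The cost is wording in two sections and one extra table. Onset is already recorded under Protocol 9.7.1, and surgery and end-of-study dates should already be collected. No visit or sample-size change is needed. The downside is that the fixed-window comparison counts fewer events, and events after day 30 appear only in the full-period table and listing.
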